7.1 STUDY INTERVENTION(S) ADMINISTRATION

7.1.1 STUDY INTERVENTION DESCRIPTION OVERVIEW

Participants will be randomized 3:1 to either pegloticase + MMF (Peg+MMF) or to pegloticase + placebo (peg+PBO).

Experimental Arm:

Participants randomized to this arm will receive pegloticase + mycophenolate mofetil.

Drug: Mycophenolate Mofetil

Participants randomized to the pegloticase + MMF arm will start on 1) Pegloticase 8 mg intravenously (IV) every two weeks, and 2) mycophenolate mofetil at 500 mg/BID and titrating up to 1000 mg/BID in 2 weeks if tolerated. Mycophenolate mofetil therapy will continue for 12 weeks at the highest tolerated dose. After the 12-week combination mycophenolate mofetil and pegloticase study period, participants will continue open-label pegloticase therapy for an additional three months.

Drug: Pegloticase 8 mg/mL [Krystexxa]

Participants randomized to the pegloticase + MMF arm will start on 1) Pegloticase 8 mg IV every two weeks#, and 2) mycophenolate mofetil at 500 mg/BID and titrating up to 1000 mg/BID in 2 weeks if tolerated. Mycophenolate mofetil therapy will continue for 12 weeks at the highest tolerated dose. After the 12-week combination mycophenolate mofetil and pegloticase study period, participants will continue open label pegloticase therapy for an additional three months. Other Name: Krystexxa

Placebo Comparator Arm:

Participants randomized to this arm will receive pegloticase + placebo

Drug: Placebo

Participants randomized to the pegloticase + placebo will receive placebo instead of mycophenolate mofetil therapy for 12 weeks. After the 12-week combination placebo and pegloticase study period, participants will continue open label pegloticase therapy for an additional three months.

Drug: Pegloticase 8 MG/ML [Krystexxa]

Participants randomized to the pegloticase + placebo will receive placebo instead of Mycophenolate mofetil therapy for 12 weeks. After the 12-week combination placebo and pegloticase study period, participants will continue open label pegloticase therapy for an additional three months.

Other Name: Krystexxa

7.1.2 DOSING AND ADMINISTRATION OF STUDY DRUGS

Mycophenolate Mofetil (MMF)

Patients will be instructed that oral dosage tablets (250 mg over-encapsulated MMF or PBO) will be administered on an empty stomach (1 hour before or 2 hours after meals) to avoid variability in Moiety Mycophenolic Acid (MPA) absorption. If a dose is missed, it will be administered as soon as it is remembered. If it is close to the next scheduled dose, the participant will be instructed to skip the missed dose and resume at the next regularly scheduled time; thus, participants will be instructed not to double a dose to make up for a missed dose.

Pegloticase

Pegloticase will be administered (per FDA approved guidelines) as an admixture of 8 mg in 250 mL of 0.45% or 0.9% Sodium Chloride Injection, USP for IV infusion over a target infusion time of 120 minutes by gravity feed or infusion pump. Pegloticase will not be administered as an IV push or bolus. Standardized IR prophylaxis consisting of pretreatment with antihistamines and corticosteroids will accompany each infusion. The drug name, dose, and timing of these prophylactic medications will be recorded.

Participants will not be fasting on the day of infusion; they will be encouraged to have a snack or normal meal 1 hour before, or immediately after, the infusion. Prior to pegloticase infusion participants will receive infusion prophylaxis (e.g. oral fexofenadine (60 mg) the night before and fexofenadine (60 mg/PO) and acetaminophen (1000 mg/PO) the morning of the infusion; and hydrocortisone IV (200 mg) immediately prior to the infusion).

In a patent IV site, using tubing with no in-line filter, the drug preparation will be infused over approximately 120 minutes (within ± 15 minutes) while the participant is under close observation for any signs of distress. Administration of drug will be immediately discontinued if respiratory distress, agitation, chest or back pain, urticaria, or another clinically significant event occurs during infusion. If the adverse event (AE) meets the definition of an serious adverse event (SAE), the infusion may not be restarted under any circumstances. A SAE will be reported within 24 hour or sooner to the Data Safety Monitoring Board (DSMB). If the AE does not meet the definition of an SAE, the site PI may make the decision to re-start the infusion depending upon the nature and severity of the AE.

Infusions subsequent to an infusion-related reaction in an individual participant may be given in a larger volume of diluent, not to exceed 500 mL. In such a case, the infusion duration will also be extended to a minimum of 3 hours. The total volume and duration of infusion will be captured in the medical record and CRF.

As a precaution, emergency equipment will be readily available to treat a possible hypersensitivity reaction, and will include drugs that would be used to treat an anaphylactic reaction. Personnel fully trained in advanced cardiopulmonary resuscitation and in the use of the emergency equipment will be readily available during, and for 1 hour after, the infusion. At the end of the infusion, the IV line will be flushed with 10 mL of normal saline to assure the full dose is administered. As IRs can occur after completion observation of participants for approximately an hour post-infusion will be performed.

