- o In rare cases in conditions (e.g. transplant, Systemic Lupus Erythematosus (SLE)) other than gout mycophenolate mofetil has been linked (incidence rate of 14.4 cases/100,000 person-years and 289/100,000 person-years respectfully) with a serious disorder of the brain known as Progressive Multifocal Leukoencephalopathy (PML). Following discontinuation of MMF patient conditions typically improve with marked reduction of weakness, and in follow-up MRI showed regression of lesions over the next 6 months. We will actively monitor participants and in the event of suspected diagnosis of PML, MMF will be withdrawn.
- Mycophenolate mofetil use is associated with increased risks of pregnancy loss and congenital malformations.

b. Pegloticase (Infusion)

i. Immediate Risks

It is common for potent urate lowering therapies to lead to acute attacks of gout. Other uncommon symptoms reported in at least 5% patients treated with pegloticase that may occur during the study period are ecchymoses, sore throat, constipation, chest pain, and vomiting. Serious allergic reactions may happen in some people while receiving infusion of pegloticase. These infusion reactions can be serious and usually happen within 2 hours of the infusion. Chest discomfort (15%), flushing (12%), and dyspnea (11%) are the most common symptoms. Symptoms associated with pegloticase infusion resolve with slowing, interrupting, or stopping the infusion. 91% of these symptoms occur in patients with serum urate concentrations greater than 6 mg/dL. Therefore, all participants serum urate will be checked prior to infusion and any participant with 2 or more serum urate test > 6 mg/dL (following initial infusion) will not be infused and will be removed from the study. Symptoms associated with infusion reactions include:

- Hemolysis; Individuals with G6PD deficiency are excluded from the study
- O Join pain 14%; Pain following injection. Pain subsides over time
- o Difficulty breathing 14%; Subsides over time
- Muscle spasms 14%; Subsides over time
- o Nausea 9%; Subsides over time
- Fever 14%; Subsides over time
- Back pain 14%; Subsides over time
- Diarrhea 14%; Subsides over time
- Erythema 14%; Subsides over time
- Hypersensitivity 14%; Subsides over time
- Rash 29%; Subsides over time
- Pain/bruising at the infusion site; Pain following injection and bruising will subside over time.

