9.3.3.3 EXPECTEDNESS

Expected potential AEs Associated with MMF (see also section 2.3.1)

- Gastrointestinal: Nausea and vomiting (12%), diarrhea
- Hematologic & oncologic: Leukopenia (renal transplant: > 50%; RA: 28%), neoplasia (renal transplant: 3% (other than lymphoma), 0.5% (lymphoma)), thrombocytopenia
- Hepatic: Hepatotoxicity, increased serum alkaline phosphatase, increased serum bilirubin, increased serum transaminases
- Infection: Increased susceptibility to infection (renal transplant 20%; RA <1%; includes bacterial, fungal, protozoal, viral, opportunistic, and reactivation of latent infections)

Expected potential AEs associated with Pegloticase (see also section 2.3.1)

During pre-marketing controlled clinical trials, infusion reactions were reported in 26% of patients treated with pegloticase 8 mg every 2 weeks. During pre-marketing controlled clinical trials, anaphylaxis was reported with a frequency of 6.5% for patients treated with pegloticase. For the purposes of this study, these events shall be defined as follows:

IR (see Section 8.3.8.1) not attributable to another cause that occurs during or within 2 hours after the

infusion of pegloticase will be defined as an AE. Other cases that occur outside of the 2-hour window may also be categorized as an IR as per site PI discretion.

- Anaphylaxis will be defined using the National Institute of Allergy and Infectious Diseases (NIAID)/ Food Allergy and Anaphylaxis Network (FAAN) criteria: acute onset of an illness (minutes to several hours) with involvement of the skin, mucosal tissue, or both (e.g., generalized hives; pruritus or flushing; urticarial, and angioedema (of lips, tongue, or uvula) and at least one of the following:
 - Hypotension (i.e., systolic blood pressure < 90 mm Hg or > 30% decrease from that person's screening)
 or associated symptoms of end-organ failure (e.g., hypotonia [collapse], syncope, incontinence)
 - Respiratory compromise (e.g., dyspnea, bronchospasm, stridor, reduced peak expiratory flow, hypoxemia)

Expected potential AEs Associated with Colchicine (see also section 2.3.1)

Participants taking colchicine for gout flare prophylaxis may experience gastrointestinal intolerance which may lead to nausea, persistent diarrhea, and/or gastrointestinal bleeding. The most commonly reported side effects for the prophylaxis of gout were diarrhea (23%) and pharyngolaryngeal pain (3%).

Other rare AEs associated with colchicine include:

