9.3.8 EVENTS OF SPECIAL INTEREST

9.3.8.1 INFUSION REACTIONS (IRS)

As described in section 8.3.3.3 during pre-marketing controlled clinical trials, infusion reactions (IR) were reported in 26% of patients treated with pegloticase 8 mg every 2 weeks. IRs will be defined as any infusion-related AE or cluster of temporally-related AEs, not attributable to another cause, which occur during or within 2 hours after the infusion of

pegloticase. Other AEs that occur outside of the 2-hour window following the infusion may also be categorized as an IR per site PI discretion. Signs and symptoms of the IR, and treatments administered, will be documented in the medical record and in the eCRF. Examples of AEs not considered possible IRs include but are not limited to: laboratory abnormalities that are unlikely to have occurred during or within 2 hours following the infusion (e.g., anemia, hypercholesterolemia), gout flares, most infectious diseases, or the recurrence or worsening of a known chronic medical problem identified in the participant's medical history.

IRs are not uncommon when biological agents are administered by IV infusion. Therefore, all participants will receive pre-treatment prophylaxis consisting of at least an antihistamine and corticosteroid prior to each infusion of pegloticase (see **Table 2**). In order to standardize this regimen, participants will take fexofenadine (60 mg, PO) the night before and again on the morning of the infusion with acetaminophen (1000 mg, PO) Prior to the infusion, hydrocortisone (200 mg, IV) will be administered and a at minimum, a targeted physical exam will be performed. The name, dose, route, date, and time of administration of each prophylactic medication will be recorded in the medical record and in the CRF.

Table 2. Infusion Reaction Prophylaxis

Night Before Infusion	Morning of Infusion	Following Arrival at Infusion Clinic
Participant takes:	Participant takes:	Abbreviated physical examination to include:
Fexofenadine (60 mg) PO	Fexofenadine (60 mg) PO	Dermatological – Noting Any Rashes
	Acetaminophen (1000 mg) PO	Chest – Noting Breath Sounds
		Vital Signs
		Start IV and Administer hydrocortisone (200 mg)
		Initiate Drug Infusion

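### Infusion reactions are defined up to 2 hours after the infusion, but planned observation ends at about 1 hour, and the schedule omits adverse event inquiry at Visits 4 and 6

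*Combined protocol and SAP*

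**What the plan says.** **Definition.** Section 9.3.8.1 counts as an IR any infusion-related adverse event (AE), without another cause, "which occur during or within 2 hours after the infusion of" pegloticase. Section 9.3.3.3 uses the same window. Beyond it, classification is left to the site PI: "Other AEs that occur outside of the 2-hour window following the infusion may also be categorized as an IR". Section 3.3.1 says of timing: "These infusion reactions can be serious and usually happen within 2 hours of the infusion". The anaphylaxis criteria in Section 9.3.3.3 allow an onset as late as several hours.

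**Observation.** Section 7.1.2 has the participant closely watched during an infusion of about 120 minutes, and then: "As IRs can occur after completion observation of participants for approximately an hour post-infusion will be performed". Personnel trained in resuscitation are "readily available during, and for 1 hour after, the infusion".

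**Later capture.** Section 9.3.4 has the investigator ask at every study visit about AEs since the previous one, and requires time of onset on the eCRF. Section 9.3.1 says participants are followed for IRs at every study visit and names IRs as a co-primary outcome. Table 1 marks AE assessment at Visits 3, 5 and 7 to 20. The Section 9 lists for Visits 4 and 6 contain laboratory items only. An unscheduled visit is planned for a suspected serious AE. Section 9.2 plans a specimen when an IR occurs.

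**The concern.** The outcome window runs about an hour past the end of planned observation. For that hour the documents describe no call, diary or same-day contact. Section 9.3.1 refers to near real-time assessment but names no procedure. A non-serious reaction that starts after discharge is then recorded only if the participant volunteers it or remembers it when next asked.

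Three things are at stake.

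- Onset time relative to the end of the infusion decides whether an event is an IR by definition or by site discretion. It would have to be recalled to the hour, possibly two weeks later.
- The specimen planned at a reaction could not be drawn at the time, and Section 10.4.3 intends to relate antibody titers to IR risk.
- The recommendation for a full-scale trial in Sections 10.4.1 and 10.4.2 is conditional on safety, so IR counts feed into it.

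Section 7.1.2 gives the possibility of reactions after completion as its reason for observing, yet stops at half of the post-infusion period used in Section 9.3.8.1.

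**Working it through.** The plan states no figure for this point, so there is none to reproduce. The check compares time windows.

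**1. Share of the window without planned observation.** Inputs: 120 minutes post-infusion in the definition (9.3.8.1); about 60 minutes observed; infusion of 120 ± 15 minutes, or at least 180 minutes after a previous reaction (both 7.1.2).

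- Post-infusion part only: (120 − 60) / 120 = 50%.
- Whole definition, infusion included: 60 / (infusion minutes + 120).

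| Infusion (min) | Whole window (min) | Unobserved share |
|---|---|---|
| 105 | 225 | 60/225 = 26.7% |
| 120 | 240 | 60/240 = 25.0% |
| 135 | 255 | 60/255 = 23.5% |
| 180 | 300 | 60/300 = 20.0% |

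**2. Time from each infusion to the next scheduled AE assessment.** Infusions fall at Weeks 0, 2, …, 22, which is 12 in all. AE assessment in Table 1 falls at Weeks 0, 2, 4, …, 24 and then in follow-up. The gap is 2 weeks after all 12 infusions. If AEs were also asked about at Visit 4 (Week 1) and Visit 6 (Week 3), as Sections 9.3.1 and 9.3.4 imply, the gap would be 1 week after the first two infusions and 2 weeks after the other ten.

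**3. Scale.** Assume, for illustration only, the 26% background IR rate of Section 9.3.3.3 in both arms.

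- Expected participants with an IR: 0.26 × 24 = 6.2 on MMF; 0.26 × 8 = 2.1 on placebo; 0.26 × 32 = 8.3 in total.
- One participant missed moves the observed rate by 1/24 = 4.2 points on MMF or 1/8 = 12.5 points on placebo.
- The documents do not give the share of IR participants whose only reaction starts in the second hour. If it were 5% to 25% (an assumption), 0.4 to 2.1 of the 8.3 would depend on later reporting, including 0.1 to 0.5 of the 2.1 on placebo. Depending on later reporting is not the same as being missed.

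**The case against.** The best defence is that the two periods serve different purposes. The 2-hour window attributes an event to the infusion; the 1-hour period is time in the clinic. The definition itself foresees later reactions and lets the site PI classify them. AE inquiry at every visit is already in the text, onset time is already collected, and a suspected serious event brings an unscheduled visit, at which an antibody sample is also listed. All of this stands. It confines the gap mainly to non-serious reactions and makes the omission at Visits 4 and 6 an inconsistency between the schedule and the text. It does not supply a procedure for the second hour.

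A reader might infer several stronger things that the documents do not support.

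- *Half of the IR window is unobserved.* Half applies only to the post-infusion part. The infusion belongs to the definition and is closely watched.
- *Reactions after the last infusion are not asked about, because Visit 17 has no IR item.* That item appears only at infusion visits. Visit 17 does assess AEs, and an IR is an AE.
- *The reported rate will be too low against 26%.* That figure is background, not a planned comparator, and how the earlier trials observed patients is not given.
- *The arms will be biased relative to each other.* The same observation rule applies to both blinded arms.

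**Conclusion.** The mismatch is real and should be corrected. About 60 of 120 post-infusion minutes, or about a quarter of the full IR definition for a 120-minute infusion, have no planned observation. On the schedule as written, the next AE assessment comes two weeks after every infusion. That second-hour events rest on later inquiry is inferred from Section 9.3.4 and the visit schedule; a participant may of course report sooner.

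The likely effect is some under-counting and imprecise onset timing of non-serious reactions in both arms, with loss of the event-time specimen for those reactions. The amount cannot be derived, because the share of reactions starting in the second hour is not documented. The 12.5 points per placebo participant show how sensitive a group of 8 is; they do not estimate a loss. It would also go too far to infer systematic under-capture or a distorted treatment comparison: safety analysis is mostly descriptive (Section 10.4.3), and no differential mechanism is shown.

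**What to change.** 1. Reconcile the observation and emergency-cover period in Section 7.1.2 with the IR window in Sections 9.3.3.3 and 9.3.8.1. The clinical investigators decide how; no period is proposed here.
2. Bring Table 1 and the lists for Visits 4 and 6 into line with Sections 9.3.1 and 9.3.4 by adding AE and IR inquiry at both visits.
3. Record the infusion end time on the eCRF, next to the AE onset time already collected, so that the interval is calculated and not judged.
4. At the next existing visit after each infusion (Visit 4, Visit 6, each infusion visit, Visit 17), ask a scripted question about symptoms after discharge on the infusion day.
5. Report IRs by arm as directly observed or recalled.

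Steps 2 to 5 need no new visits. The cost is a protocol clarification, one time field, one question, a label in the safety tables and slightly more data entry. The reported IR rate may come out slightly higher.

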7.2 PREPARATION/HANDLING/STORAGE/ACCOUNTABILITY OF STUDY DRUGS

7.2.1 ACQUISITION AND ACCOUNTABILITY

Pegloticase will be shipped by Horizon Pharma, PLC to the study sites. The UAB IDS Pharmacy will be responsible for the storage, over-encapsulation, and shipment of mycophenolate mofetil and placebo pills for this study. MMF will be purchased in bulk quantity through the UAB Investigational Drugs Pharmacy, which will also oversee the process of overencapsulation with cellulose of the active medication and placebos, handle medication storage, distribution, and assignment of randomization sequence. A drug log will be used to track the study drug from pharmacy to each randomized study participant. The centralized management of the medication will allow maintenance of a double-blind trial. Adherence to the medication will be recorded by pill counts at the follow-up study visits and consumption of at least 80% will be required to consider the participant compliant. A non-compliant participant will continue in the study and enter analyses as mandated by statistician. Further questions about pharmacy activities can be directed to: [name]; IDS Pharmacy, University of Alabama at Birmingham Hospital, [contact].

Supplies and medication vials used in preparing medications will be discarded as waste immediately after product preparation. The waste is incinerated on-site at UAB Hospital and UM hospital. In addition, incineration is the method of destruction for expired, returned and unused product at study closure. When a study is closed or closed to enrollment (and no participants are being treated), sites will have 60 days to document destruction of unused product.

7.2.2 FORMULATION, APPEARANCE, PACKAGING, AND LABELING

Mycophenolate Mofetil (MMF)

MMF, the immune modulator for the study, is the 2-morpholinoethyl ester of moiety mycophenolic acid (MPA), and is an inosine monophosphate dehydrogenase (IMPDH) inhibitor. The chemical name for MMF is 2-morpholinoethyl (E)-6-(1,3-dihydro- 4-hydroxy-6-methoxy-7-methyl-3-oxo-5-isobenzofuranyl)-4-methyl-4-hexenoate. It has an empirical formula of C₂₃H₃₁NO₇. MMF will be purchased by UAB from Besse Medical (West Chester Township, OH). MMF capsules include croscarmellose sodium, magnesium stearate, povidone (K-90) and pregelatinized starch. The MMF capsule shells contain black iron oxide, FD&C blue #2, gelatin, red iron oxide, silicon dioxide, sodium lauryl sulfate, titanium dioxide, and yellow iron oxide. All MMF capsules will be over-encapsulated with cellulose to match compounded placebo. Favorable pharmacokinetic properties of the encapsulation process have been consistently noted with other substances. Blinded study drug labeling will be annotated with the protocol number by the research pharmacist. The UAB site pharmacy will maintain an inventory of drug supplies received and dispensed.

Pegloticase

Pegloticase (Krystexxa®) is a clear, colorless, sterile solution in phosphate-buffered saline intended for IV infusion after dilution and will be supplied by Horizon Pharma, PLC. Pegloticase is commercially available in the US in a single-use, 2 mL glass vial with a Teflon coated (latex-free) rubber injection stopper. Each mL of pegloticase contains 8 mg of uricase protein conjugated to 24 mg of 10 kDa monomethoxypoly (ethylene glycol). Excipients include disodium hydrogen phosphate dihydrate, sodium chloride, sodium dihydrogen phosphate dehydrate, and water for injection. All participants in the study will receive pegloticase at the same dose of 8 mg administered IV every 2 weeks for a total of 6 infusions over a 12-week treatment period, and over an additional 12-week pegloticase opt-in follow-up period (per standard of care). Study drug labeling will be annotated with the protocol number.

